6.7 Echocardiography

An echocardiogram will be performed at the screening visit as well as the 1 month visit. Echocardiography will be performed to measure the size and shape of the heart, its chambers and blood flow as well as valvular structure and function. Additionally, the echocardiogram will be used for detection of any wall motion abnormalities indicative of myocarditis.

The quantitative echocardiographic data points must include:

- End Diastolic Volume
- End Systolic Volume
- Ejection Fraction
- LV End Systolic Diameter
- LV End Diastolic Diameter

6.8 24 Hour Ambulatory ECG Monitor

A 24 hour ambulatory ECG monitor will be performed at the screening visit, during the 24 hours following release (discharge) from the hospital and also at the 1 month, 6 months and 12 months study visits. Subjects enrolled in the Safety Cohort will also have the test performed at the 2 months study visit. The monitor is used to detect and record arrhythmia. All changes and any associated clinical significance will be evaluated and documented on the case report form.

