7.3.6 Month 12 Visit (Day 360 ± 6 days) Procedures

Subjects will undergo multiple assessments 12 months after intracoronary infusion, including:

- Limited physical examination and cardiac physical examination
- Medication review
- Adverse events assessment
- Vital signs
- 12-Lead ECG
- Laboratory tests: hematology, chemistry, urinalysis, DSA monitoring, serum NT-proBNP; refer to [Table 1](#) for comprehensive list of laboratory tests
- Serum for biomarkers (if subject has provided consent)
- Cardiac MRI
- 24 hour ambulatory ECG recording
- NYHA functional class assessment
- Six Minute Walk Test
- MLHFQ
- SF-36 health survey
- WPAI:SHP questionnaire
- Patient Global Assessment

If subjects undergo inter-current ICD/pacemaker placement, study imaging sites must be trained and certified specifically for this protocol prior to conducting cardiac MRI in subjects with ICD and/or pacemaker placement. If subjects develop MRI contraindications, a cardiac MRI will not be performed. Such subjects will continue to be followed in the study and undergo all 12 month

study procedures except MRI. Any subject whose GFR declines to <30 mL/min during a given MRI study will not undergo contrast administration on this and subsequent MRI studies. Such treated subjects will not be withdrawn but will still be followed for inclusion in safety and efficacy analyses for other parameters assessed during the study.

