¹ Permitted within 28 days immediately following index MI: signing ICF, review of medical history, review of concomitant medications, and collection of laboratory samples required for assessment of study eligibility criteria (e.g., eGFR, HbA1c, hepatitis serology, HIV serology, LFTs, hematocrit, WBC, serum β-HCG and platelet count).

² Must be performed >28 days post-MI and ≤28 days of infusion. Repeat hematology, chemistry & urinalysis if initial testing to assess eligibility falls outside of this window. For post infusion, urinalysis only.

³ Every 8 hours from time of infusion until discharge.

⁴ On day of discharge.

⁵ Urinalysis only.

⁶ For subjects on anticoagulation therapy only.

⁷ Only if additional consent is obtained; collection for shipment to central laboratory.

⁸ Non-postmenopausal females only.

⁹ Troponin and CK-MB pre-infusion and approximately every 8 hours post infusion.

¹⁰ Collection of blood for testing at central laboratory.

¹¹ Starting immediately prior to discharge for 24 hours.

¹² MLHFQ, SF-36, WPAI:SHP and Patient Global Assessment.

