### **2.3.3 Secondary Safety Endpoints**

The following adjudicated (see [Section 12](#)) events will be evaluated as secondary safety endpoints over the twelve-month follow-up period:

1. Acute myocarditis possibly attributable to the IP, diagnosed with consideration of clinical

context, with or without a clinically indicated endomyocardial biopsy. In order to be considered related to the IP, humoral or cellular immune reaction specific to CAP-1002 must also be documented for subjects treated with CAP-1002, or a temporal relationship with IP administration must exist for subjects administered placebo. See [Section 12](#) for further information related to blinded adjudication by the CEC.

2. Death due to ventricular tachycardia or ventricular fibrillation defined as occurring with prior ECG documentation of these arrhythmias during ambulatory ECG monitoring in an outpatient setting or during routine ECG monitoring while hospitalized.
3. Sudden unexpected death defined as occurring within one hour of symptom onset, or un-witnessed death in a person previously observed to be well within the preceding 24 hours without an identified cause.
4. MACE, as defined above.
5. New cardiac tumor formation on magnetic resonance imaging (MRI).
6. Any hospitalization due to a cardiovascular (CV) cause or related to IP infusion.
7. Any inter-current CV illness, or one related to IP infusion, which prolongs hospitalization. Evidence of myocardial injury will be assessed by a rule out MI cardiac enzyme protocol performed following IP administration. Troponin and CK-MB will be obtained approximately every 8 hours for the first 24 hours after infusion.
8. New TIMI flow  $\leq 1$  following IP infusion.
9. Development of, or an increase in the frequency of, ventricular tachycardia with a duration of 30 beats or longer ascertained by periodic, protocol-mandated 24 hour ambulatory ECG monitoring.

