## 10.2 Secondary Safety Endpoints

The secondary safety endpoints include clinical events, as described in [Section 2.3.3](#). The secondary safety endpoint listing will include indicators for each event, study day of the event, and total days of follow-up. Each endpoint will be summarized as frequency of subjects who experienced the endpoint and event rate per 100 subject-years. The summary table of the clinical event endpoints will also include a p-value for the comparison of event rate between treatment groups based on negative binomial regression with an offset for days of follow-up (log transformed). If the dispersion parameter is not significantly different from zero, Poisson regression will be used instead. Since the clinical event endpoints account for differential length of follow-up, handling of missing data is not applicable.

For the analysis of the secondary safety endpoint of development of increased HLA antibody levels to HLA antigens specific to the CAP-1002 CDC donor, incidence of increased HLA antibody levels, specific to the donor, will be summarized and analyzed; for placebo subjects, a random donor will be selected from those that were matched to the subject during screening. Elevated levels of DSA will also be summarized and analyzed by time point for all nominal time points at which samples were collected for DSA testing. Analyses will be performed using both 5000 and 1000 MFI as the threshold for defining increased HLA antibodies.

One secondary safety endpoint, new TIMI flow  $\leq 1$ , would only occur intra-procedurally and will be analyzed using a chi square or Fisher's exact test instead of negative binomial or Poisson regression.

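### SAP 10.2 counts every day of follow-up as exposure for a VT endpoint that is seen only on four 24-hour recordings, so a missed recording becomes event-free time

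*SAP*

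**What the plan says.** SAP 2.3.3, item 9, ties the endpoint to one means of detection: "ventricular tachycardia with a duration of 30 beats or longer ascertained by periodic, protocol-mandated 24 hour ambulatory ECG monitoring". An event counts if VT of that length is new or has become more frequent.

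Protocol 6.8 schedules a screening recording, then recordings "during the 24 hours following release (discharge) from the hospital and also at the 1 month, 6 months and 12 months study visits". The extra Month 2 recording is for the Safety Cohort only. The first post-infusion recording is described in a footnote to Protocol Appendix 1: "Starting immediately prior to discharge for 24 hours". A randomized subject therefore has four post-infusion recordings.

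SAP 10.2 sets one rule for the secondary safety endpoints: "Each endpoint will be summarized as frequency of subjects who experienced the endpoint and event rate per 100 subject-years". Clinical events are then compared by "negative binomial regression with an offset for days of follow-up (log transformed", or by Poisson regression if there is no overdispersion. On missing data it says: "Since the clinical event endpoints account for differential length of follow-up, handling of missing data is not applicable".

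Two endpoints are treated differently in the same section. TIMI flow is moved to a chi-square or Fisher's exact test because it can occur only during the procedure, and donor-specific HLA antibodies have their own incidence and by-time-point analysis. VT has no exception.

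**The concern.** An offset for follow-up time is right when an event can be counted on any day of follow-up. That holds for death or hospitalization. It does not hold for an endpoint that exists only if a recorder is running. Days between recordings add to the denominator but can never add to the numerator.

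The missing-data statement has the same weakness. A subject who attends visits but has no recording is still in follow-up, so the length of follow-up does not register the gap. The model then treats unobserved time as observed and free of VT.

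What is at stake is the reading of an arrhythmia signal for an intracoronary cell product. Protocol 7.7 lists ventricular tachycardia among the events to be examined more closely, and SAP 13.1 sends the secondary safety endpoints to each DSMB review.

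**Working it through.** The documents give no VT rate, event count or power for this endpoint, so there is no plan figure to reproduce. The check compares the exposure used with the time monitored.

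**Inputs**
- Post-infusion recordings: 4, of 24 hours each (Protocol 6.8 and Appendix 1), so 4 monitored days.
- Follow-up for a completer: 360 days, from "Month 12 Visit (Day 360 ± 6 days) Procedures", with a window of Day 354 to 366.
- Follow-up length: SAP 10.2 does not define it. The only formula in the SAP is in 8.9: date of last known status minus infusion date plus 1, taken from adverse event, medication, visit and end-of-study dates. Whether a recording was made plays no part.

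**Exposure ratio = follow-up days / recorded days**
- Completer, all four recordings: 360/4 = 90 (354/4 = 88.5 to 366/4 = 91.5).
- Completer with 3, 2 or 1 recordings: 120, 180 or 360.
- Exit at Day 30 with 2 recordings: 30/2 = 15. Exit at Day 180 with 3: 180/3 = 60.

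The ratio is not constant, so the offset is not merely a change of units.

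**Missed recordings.** Suppose the true rates are equal, follow-up is the same in both arms, and detection is proportional to the number of recordings. The planned rate ratio is then the ratio of mean recordings obtained. The completion figures below are assumptions.

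| Mean recordings, arm A / arm B | Planned rate ratio (true value 1) |
|---|---|
| 4 / 4 | 1.0 |
| 3.5 / 4 | 0.875 |
| 3 / 4 | 0.75 |
| 2.5 / 4 | 0.625 |

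**Early exit.** If a fraction f of one arm leaves at Day 30 with 2 recordings, and nobody leaves the other arm, the ratio is [(4(1−f) + 2f) / (360(1−f) + 30f)] / (4/360). For f = 5%, 10% and 20% (assumed) this is 1.02, 1.05 and 1.10.

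**Across reviews.** Recordings cluster early. With a constant chance of detection per recording, the expected rate for a subject followed to Day 30, relative to one followed to Day 360, is (2/30)/(4/360) = 6. A pooled rate can therefore fall as follow-up accrues with no change in risk.

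**Does 90 measure the understatement of VT?** Only if episodes are counted and occur at a constant rate. Take an assumed 5 of 69 CAP-1002 completers with VT:
- per follow-up time: 5/(69 × 360/365.25) = 7.4 per 100 subject-years;
- per monitored time: 5/(69 × 4/365.25) = 662 per 100 subject-years.

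If the 5 are subjects and the hazard is constant, the 360-day proportion is 1 − (1 − 5/69)^90, about 0.999. Against the observed 0.0725 that is a factor of about 14, not 90. Over an assumed 0.1% to 20% of subjects seen with VT, the factor runs from 86 down to 5. If risk also varies between subjects (gamma frailty with shapes 0.05 to 1, and 2% to 10% seen), it is about 3 to 32.

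**The case against.** Both arms follow the same recording schedule, so with equal completion the exposure ratio drops out of the comparison. The planned figure can then be read as detected events per subject-year under a common schedule. Subjects and investigators are blinded, which makes a large arm difference in completion hard to motivate. A 5-point difference (95% against 100%) would give a ratio near 0.95, small beside sampling error with a handful of events. The endpoint is secondary, and the protocol synopsis calls these analyses descriptive. SAP 10.2 also reports the number of subjects with the event, SAP 10.9 summarizes a VT indicator from the same recordings, and SAP 11.1 lists missed assessments.

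Most of this stands as a limit on size, but it does not repair the rule. SAP 10.9 states no 30-beat threshold and no new-or-increased criterion. A listing of missed assessments does not enter the rate or the test. The number of subjects is given with no evaluable set.

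Three stronger readings are not supported:
- A reader might infer that the plan understates the VT rate 90-fold. The 90 is a completer's exposure ratio. SAP 10.2 does not say whether subjects, positive recordings or episodes are counted, and on a subject count the understatement is smaller.
- A reader might infer that the treatment comparison is already biased. That needs unequal completion or unequal early exit, and the documents show neither.
- A reader might infer that VT outside the recordings goes unreported. Arrhythmic death, cardiovascular hospitalization and treatment-emergent adverse events are captured separately.

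**Conclusion.** The point holds for this one endpoint. The exposure in SAP 10.2 is about 90 times the monitored time for a full completer, and the reason given for not handling missing data is wrong here, because follow-up length does not reflect whether a recording was made. Unequal completion shifts the rate ratio toward making the arm with more missed recordings look safer: 0.875 or 0.75 for a mean of 3.5 or 3 recordings against 4. Those figures rest on assumed completion, equal true rates and equal follow-up. With equal completion and equal follow-up patterns the comparison is unaffected, although the absolute rate still does not describe VT per unit of observed time. It is worth correcting because the change is cheap and the data are already collected.

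**What to change.** For endpoint 9 in SAP 10.2:

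1. Replace the offset for days of follow-up with recorded hours, or with the number of evaluable recordings, and state what is counted. As an alternative or in addition, report by visit the number and percent with VT of 30 beats or longer that is new or increased from screening, among subjects with a screening recording and a readable recording at that visit, with an exact comparison.
2. Tabulate completed recordings by arm and visit.
3. Remove the statement that missing-data handling does not apply, for this endpoint.

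A single overall percent among subjects with at least one evaluable recording is not enough. If every subject in one arm has 3 of 4 recordings, all still qualify and the ratio stays near 0.75. If recordings are missed independently at 25%, only 0.25^4 = 0.4% of subjects are excluded.

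Both forms in step 1 still assume that missed recordings are unrelated to VT risk; the completion table lets a reader judge that. The exact comparison also moves toward the protocol synopsis, which names Fisher's exact test for secondary safety incidence rates, while SAP 14 declares no deviations.

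The cost is SAP wording, one extra table and slightly smaller denominators. Recording start and end times are already listed under SAP 10.9, so no new data are needed.

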The Exploratory Randomized Cohort will enroll up to 17 subjects in addition to the Primary Randomization Cohort. Exploratory Randomized Cohort subjects are those subjects who are mismatched against all available donors. The Exploratory Randomized Cohort will also include Recent and Chronic subjects (up to n=8-9 per stratum). The Exploratory Randomized Cohort will be randomized in a double-blind fashion as described in the Primary Randomized Cohort. The Exploratory Randomized Cohort will undergo the same tests as all other subjects based on the schedule of events. This group will be analyzed separately from the Primary Randomized Cohort using descriptive analyses to assess the prevalence and impact on safety and efficacy, if any.

[figure not shown]
The Primary Randomized Cohort will consist of up to approximately 103 subjects who can be matched to receive IP from one or more donor. A match is achieved when a subject is found at screening to have no antibodies against a donor's HLA antigens (i.e. no donor specific antibodies [DSAs]). Subjects that are mismatched to all available donors will be enrolled into a Phase II Exploratory Randomized Cohort to gather information on potential differences in safety/efficacy. A mismatch situation occurs when a subject is found at screening to have DSAs against all available donors. Up to 17 subjects will be enrolled into the Phase II Exploratory Randomized Cohort.

These Exploratory Randomized Cohort subjects will be randomized independently from the Primary Randomized Cohort. The Exploratory Randomized Cohort is designed to assess the potential effect of donor mismatching, if any, on the primary safety and efficacy endpoints. Using a distinct arm in the study design allows for the inclusion of all subjects meeting eligibility criteria, but preserves the design integrity of the Phase II Randomized Cohort.

Study Population:

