10. Development of increased anti HLA antibody levels with development of sensitization to HLA antigens specific to the CAP-1002 CDC donor. Elevation of donor-specific antibodies (DSA), using the LABScreen® single-antigen in vitro diagnostic assay that is a Luminex® based antibody detection assay designed to detect Class I or Class II HLA antibodies in human serum or plasma, is defined as mean fluorescence intensity (MFI) above a threshold of 5000; a threshold of 1000 MFI will also be used to evaluate elevation of DSA. See [Section 12](#) for further information related to blinded adjudication by the CEC and [Section 10.2](#) for details related to comparison to placebo.

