### **3. STUDY DESIGN AND SCHEDULE OF EVENTS**

This is a randomized, double-blind, placebo-controlled phase 2 trial designed to evaluate the safety and efficacy of intracoronary delivery of CAP-1002 in subjects with ischemic LV dysfunction and a previous MI. Detailed inclusion and exclusion criteria are in Section 4 of the protocol.

Approximately 120 subjects with a previous anterior MI and resultant ischemic LV dysfunction who meet all inclusion and exclusion criteria will be enrolled into one of two cohorts: the Primary Randomized Cohort and the Exploratory Randomized Cohort. The Primary Randomized Cohort will include approximately 103 subjects who meet compatibility to receive IP from one or more donor(s). Compatibility is achieved when a subject is found at screening to have no pre-existing antibodies against a donor's HLA antigens (i.e., no DSA). The remaining subjects (approximately 17) who have pre-existing antibodies against all available donors will be enrolled in the Exploratory Randomized Cohort so that potential differences in safety and efficacy can be assessed. Each of the two cohorts will be randomized separately. Subjects will be randomized within strata defined by time since MI ("recent" or "chronic") to receive CAP-1002 or placebo in a 2:1 ratio favoring CAP-1002. "Recent" will be defined as more than 4 weeks but within 90 days prior to randomization and "chronic" will be defined as more than 90 days but less than 12 months prior to randomization. Enrollment in the study will end when approximately 130 subjects have been randomized.

Subjects will undergo protocol assessments through 12 months post infusion. Reviews by a Data Safety Monitoring Board (DSMB) will be done per charter at least semi-annually. The DSMB will review both safety and efficacy data after all subjects complete 6 months of follow-up or withdraw from the study. In addition, there will be one administrative interim efficacy analysis after Month 6 MRI measurements are available for all subjects. An additional administrative efficacy analyses may be done on an as-needed basis. Subjects will be followed annually for 5 years post infusion or reference date.

The Schedule of Events is shown in [Appendix A](#).

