## 5. RANDOMIZATION AND BLINDING

The following are required for subject randomization to occur:

- Trigger from site via electronic data capture (EDC) that a subject is ready for randomization.
- Analysis of blood samples to determine cohort assignment (Primary or Exploratory) based on presence or absence of DSA to available donors.
- Identification of donor cell lines for which the subject is compatible.
- Strata membership: recent MI (“Recent”) or chronic MI (“Chronic”).

The Primary Randomized Cohort and the Exploratory Randomized Cohort will be randomized separately. Subjects will be randomized 2:1 CAP-1002:placebo within each stratum using random block sizes of 3 and 6 and institutional balancing in an interactive web-based system (IWRS). Notification that a subject has been randomized will be sent to an independent storage/distribution center (depot). The depot will have password protected access to the randomization assignment and will randomly assign subjects in the Primary Randomized Cohort to an appropriate donor (or placebo). Subjects in the Exploratory Randomized Cohort will be randomly assigned to one of the available donors regardless of compatibility (based upon available inventory).

Both investigators and subjects will be blinded to treatment assignment throughout the trial. Core and central laboratory personnel analyzing the MRI images and testing serum for serial donor specific antigen and whole blood for cellular immune response will also be blinded throughout the trial, as will the CEC adjudicating events, and all medical affairs and clinical operations staff, except as noted below. Personnel at the MRI core laboratory will be blinded to treatment assignment but not temporal order of the images; e.g., readers will have access to and will use baseline and Month 6 images when reading Month 12 images as part of the informed reading protocol. A member of the Sponsor staff will be unblinded if an emergency blind break is required at any time during the trial. Study sites will be trained regarding the emergency unblinding process. Should a medical event occur that necessitates unblinding, the process will be accessible to investigators 24 hours a day and will include an emergency Sponsor contact.

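### The donor-antibody endpoint scores an absolute level, not a change from screening, and its placebo donor rule returns no donor in the Exploratory Cohort

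*SAP*

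**What the plan says.** SAP 2.3.3, item 10, names the endpoint as "Development of increased anti HLA antibody levels with development of sensitization to HLA antigens specific to the CAP-1002 CDC donor". The same item gives the working rule: elevation of donor-specific antibody (DSA) "is defined as mean fluorescence intensity (MFI) above a threshold of 5000; a threshold of 1000 MFI will also be used". SAP 10.2 confirms it: "Analyses will be performed using both 5000 and 1000 MFI as the threshold for defining increased HLA antibodies". Neither section asks for a rise, or for a screening value at or below the cut-off.

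On the reference donor in the control arm, SAP 10.2 says "for placebo subjects, a random donor will be selected from those that were matched to the subject during screening". It makes no exception by cohort.

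The Exploratory Cohort is defined by the absence of a match. The Protocol synopsis says "A mismatch situation occurs when a subject is found at screening to have DSAs against all available donors", and SAP 3 says that the subjects "who have pre-existing antibodies against all available donors will be enrolled in the Exploratory Randomized Cohort". On donor allocation, SAP 5 says "Subjects in the Exploratory Randomized Cohort will be randomly assigned to one of the available donors regardless of compatibility". Protocol 5.2 describes the same step, placed after the 2:1 assignment to CAP-1002 or placebo.

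On use of the endpoint, SAP 10 puts the primary analysis in the primary safety population and makes other populations optional. SAP 7.2 promises some outputs for the Exploratory Cohort without naming them. Protocol 2.5.1 commits to a descriptive comparison of safety between the two cohorts.

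**The concern.** The label describes something that develops after infusion, while the scoring rule describes a level at a visit. The two agree when everyone starts low. They part company in a cohort selected for having antibody to every donor before treatment. There, an antibody that was high at screening and did not move is scored in the same way as one that the cells provoked.

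The control arm has a separate gap. A placebo subject needs a reference donor before any MFI can be read as donor-specific, and the only rule in 10.2 picks from matched donors.

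What is at stake is the descriptive picture of how pre-existing antibody affects safety. If the rule is applied as written, the cohort's antibody event rate partly reflects who was enrolled, and its placebo rate is undefined.

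**Working it through.** **1. Cohort size.** Inputs from Protocol 9.2: 103 matched subjects, 14% mismatch.
- Screened: 103 / (1 − 0.14) = 119.8, rounded up to 120, as stated.
- Mismatched: 120 × 0.14 = 16.8, rounded up to 17, as stated.
- At 2:1: 17 × 2/3 = 11.3 on CAP-1002 and 17 × 1/3 = 5.7 on placebo, so about 11 and 6. The 17 is a cap, so these are upper figures.

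**2. Placebo reference donor.** With K available donors, a subject mismatched to all of them has K − K = 0 matched donors. The 10.2 rule therefore gives a donor to 0 of about 6 Exploratory placebo subjects.

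**3. Events present before infusion.** Let q be the share of Exploratory subjects whose screening MFI to the assigned donor exceeds the cut-off, and assume that the level persists after infusion. The expected number of such events in the CAP-1002 arm is 11 × q. The documents do not give q, so these values are assumptions:

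| q | 11 × q |
|---|---|
| 0 | 0 |
| 0.10 | 1.1 |
| 0.25 | 2.8 |
| 0.50 | 5.5 |
| 1.00 | 11 |

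The MFI level that makes a subject mismatched is not stated. SAP 7.4 lists baseline DSA bands of under 500 and 500–1000, which would fit a matching limit of 1000. If that was the limit, q is 1 at the 1000 cut-off. At 5000, q stays unknown and could be 0.

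**4. Effect on the comparisons.** Let r be the rate of new crossing among subjects who start below the cut-off.
- Exploratory CAP-1002 rate under the present rule: q + (1 − q)r.
- Primary Cohort CAP-1002 rate: about r. Those subjects had no DSA to their donor, so their q is near 0, provided the matching limit is no higher than the cut-off.
- Gap between cohorts when mismatch changes nothing: q + (1 − q)r − r = q(1 − r). At q = 0.25 and r = 0, that is 0.25, or about 3 of 11 subjects.
- If Exploratory placebo subjects are given a random donor, q is the same in both arms in expectation. The difference between arms becomes (1 − q) times the difference in r. It is diluted but not pushed in one direction.

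**5. Does another section repair the rule?** SAP 10.2 also summarises elevated DSA by time point, and SAP 10.5 plans changes from baseline for laboratory groups that include DSA monitoring. Both would show baseline levels, but neither changes who counts as an event. SAP 2.3.3 points to Section 12 for adjudication. Section 12 lists this endpoint as an exception to committee adjudication and says only that the DSMB immunologist sees the DSA data.

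**The case against.** The strongest case against is that the rule was written for the primary safety population, where every subject has at least one matched donor and it works. The Exploratory Cohort is descriptive, and no section commits to a between-arm test of this endpoint in it. The endpoint's own words could be read as requiring something new, with the MFI cut-off defining only elevation. A subject who was positive at screening would also be visible in the DSA listing.

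Most of this stands as a limit on size. It does not close the gap. The protocol does commit to comparing safety between cohorts, and SAP 10.2 states that the cut-offs are what define increased antibody. A programmer following it would not test the screening value.

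Some stronger readings are tempting but not supported:
- *Exploratory placebo subjects cannot be scored at all.* Protocol 5.2 and SAP 5 can be read as giving every Exploratory subject, placebo included, a nominal donor from the available pool. Section 10.2 simply does not use it.
- *The primary analysis is compromised.* Its subjects are matched at screening, so an elevation after infusion is essentially new.
- *This is the cohort's main endpoint.* The synopsis ties the cohort to the primary safety and efficacy endpoints. This endpoint is secondary.
- *Many Exploratory events will be automatic.* That depends on q, which is not given.

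**Conclusion.** The point holds and is minor. As written, endpoint 10 scores a level under a label that promises a change, and the placebo donor rule has nothing to select from in the Exploratory Cohort. At most 17 subjects are affected: about 6 placebo subjects have no reference donor under 10.2, and between 0 and 11 CAP-1002 subjects would be scored as events on antibody that they brought with them. Where in that range the true figure falls depends on the unstated screening MFI distribution and on persistence of the antibody after infusion. The primary analysis of this endpoint should change little, assuming the matching limit does not exceed 1000 MFI.

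**What to change.** In SAP 2.3.3 item 10 and SAP 10.2:
- Count an event only if a post-infusion MFI to the reference donor exceeds the cut-off and the screening MFI to that donor did not. Apply this at both 5000 and 1000.
- For subjects already above the cut-off at screening, report change from baseline separately, or use a rise criterion whose value the sponsor fixes in advance. Keep the plain cut-off as a second display.
- For Exploratory placebo subjects, use a reference donor drawn at random from the available donors, as for the CAP-1002 arm. If the donor step in Protocol 5.2 and SAP 5 already recorded one, say that it is the donor used.

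The cost is a few sentences. DSA is already drawn at screening and at week 2 and months 1, 3, 6 and 12, so no new samples are needed. The drawback is a smaller group at risk: at q = 0.50, only about 11 × 0.50 = 5.5 Exploratory CAP-1002 subjects could register a new crossing. That denominator should be shown beside the event count.
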